Study 2 manipulates the location and orientation of the coil during rTMS of MT to bias rTMS effects either *toward the dorsal pathway (rTMS-D)* or *toward the ventral pathway (rTMS-V)*. Positioning parameters are chosen by integrating information about (1) white-matter connectivity for ventral/dorsal pathways from MT, and (2) the induced E-field from MRI-based individual head models and its relationship to functional activity. First, fMRI maps are used to select the stimulation site, which is the seed point for E-field estimation. Next, DWI tractography estimates from the stimulation site, MT, are used to define trajectories of fiber tracts from MT into the dorsal pathway, specifically to FEF, or into the ventral pathway, specifically to the anterior temporal lobe. Then, structural scans (T1- and T2-weighted) are used for E-field modeling to select the best coil orientations for aligning the E-field distribution along the dorsal or ventral pathways identified above on an individual basis.

Thus, Study 2 uses 3 spatial conditions for rTMS stimulation. Each of the 3 conditions is assigned to four blocks of 20 trials each (80 trials/condition); each trial lasts 10 seconds, and we will administer 12 blocks (40 minutes, 240 trials total) in both the TMS-fMRI and TMS-EEG experiments. The TMS-fMRI and TMS-EEG will necessitate 60 minutes preparation to adjust the positioning for the TMS coil and—in the TMS—EEG experiment—apply the EEG cap, as well as 30 minutes for a brief rTMS side effect rating scale and visual analog mood ratings will be administered before and after each rTMS block. Thus, the entire session will last 3 hours for both the TMS-fMRI and TMS-EEG Session. As above, subjects' side effects will be monitored closely.

Study 3

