EEG analyses. Pre-processing of EEG includes bad channel replacement, temporal filtering, and ICA analyses to remove artifacts. EEG analyses use either repeated-measures ANOVAs or non-parametric methods (Maris and Oostenveld, 2007b, a) to infer amplitude and latency effects on relevant ERP components and/or sources, as described in each study. Coherence analyses are performed to estimate inter-channel connectivity, with planned analyses on cross-hemispheric and anterior-posterior associations. As done in our past studies, (Appelbaum et al., 2006; Appelbaum et al., 2008; Appelbaum et al., 2010; Ales et al., 2012; Appelbaum et al., 2012) depth-weighted minimum norm analyses will be performed using MRI-derived finite element head models calculated for each participant following alignment of electrode positions to the MRI head surface. Head models are based on compartmentalized tissue segmentations that defined contiguous regions for the scalp, outer skull, inner skull, and the cortex. Cortically constrained minimum norm source estimates are determined by a linear optimization of dipole magnitudes with the least total (root mean square) power while lead field normalization is used to compensate for the inherent bias toward superficial sources.

Specific Study Analytical Procedures

Study 1

TMS data: Mixed model ANOVAs with repeated-measures factors of Frequency (1Hz/5Hz/10Hz), and Number of Pulses (3/15/30 pulses), and rTMS (target, sham [vertex] stimulation) will be performed separately on the median RT and accuracy data. Power analysis shows that 30 subjects/group should be sufficient to see a medium sized effect at an alpha of 0.05. In our previous studies using a Working Memory task with active and sham rTMS over multiple sites, letter set sizes, and task phases, groups of 21 (Luber et al., 2007) 15 (Luber et al., 2008) and 26 (Luber et al., 2013) were sufficient to produce significant effects at the 0.05 level.

[figure not shown]
Study 2

DWI fiber tracking. Our DWI tractography methods have been reported (Davis et al., 2009). For a priori tracts connecting the MT cortex, we use TrackVis (trackvis.org) to identify MT and all connecting regions (FEF, IPS). (Kier et al., 2004b, a) FA values are extracted and analyzed using standard statistics.

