Modeling: Head regions are extracted from MRI images, then up-sampled, reoriented, corrected for bias field inhomogeneity, filtered with content-preserving anisotropic diffusion filters, and automatically segmented with software (including gray matter, white matter, and CSF using SPM). High resolution triangular surface meshes of the head model (SimNIBS) are used to compute the E-field (Windhoff et al., 2013). A detailed model of the TMS coil is added to the head model (Fig. 2, center). Isotropic tissue conductivities are assigned to the various tissue compartments.(Opitz et al., 2011) Optionally, we can include anisotropic conductivity in the white matter based on the DWI data, although the impact of white matter anisotropy is small for TMS which affects predominantly superficial cortex (Opitz et al., 2011; Lee et al., 2012). The E-field is computed with a harmonic solver in Maxwell using FEA and scaled in post-processing for the specific pulse shape and amplitude (Deng et al., 2011). **Using the models for targeting:** For SCR in the TMS-induced E-field, the TMS coil will be oriented so that the modeled E-field is normal to the sulcal wall nearest to the recording target to achieve strongest neural activation (Janssen et al., 2014, 2015). For TMS during fMRI or EEG, the peak voxel of fMRI task activation (Session 2) will be used as the center of a 3×3 (A-P and L-R) grid for positioning the coil in simulations of the E-field (Fig. 2, right) corresponding to these 9 coil positions and 6 orientations (54 combinations). The simulation E-field maps will be extracted and correlated, voxel-to-voxel, with the fMRI activation to determine an optimal coil orientation and position. The simulation that yields the highest correlation is selected the optimal coil position and orientation.

Study 3

fMRI Analyses: All EEG, fMRI and behavioral analysis approaches described above will be implemented. However, a unique feature of Study 3 is that it will examine multiple brain states (motor task, color task, rest), while Study 1 and 2 focus on the motor task along. We will therefore capture the cross-task similarities using Independent Components Analysis (ICA), which is useful for identifying consistent relationships between disparate datasets.

TMS data: Mixed model ANOVAs with repeated-measures factors of Site (2 scalp locations, target or vertex), and Brain State (color, motion task, or rest) will be performed separately on the median RT and accuracy data.

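### Study 2 has two unreconciled coil-placement rules: alignment with dorsal or ventral tracts in Section 4, and the single best correlation with fMRI activation in Section 12

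*Combined protocol and SAP*

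**What the plan says.** Section 4 (Study 2) gives a sequence for each participant. fMRI maps select the stimulation site. DWI tractography from MT then defines a dorsal trajectory to FEF, "or into the ventral pathway, specifically to the anterior temporal lobe". Structural scans and E-field modeling are then used to "select the best coil orientations for aligning the E-field distribution along the dorsal or ventral pathways identified above on an individual basis". The section states that there are three spatial conditions. From the prediction in Section 2, these are rTMS-D, rTMS-V and a control.

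Section 12 (Study 2, E-field Modeling, the part on using the models for targeting) gives another rule. Its scope and starting point are: "For TMS during fMRI or EEG, the peak voxel of fMRI task activation (Session 2) will be used as the center" of a 3×3 grid, with simulations "corresponding to these 9 coil positions and 6 orientations (54 combinations"). The score is then defined: "The simulation E-field maps will be extracted and correlated, voxel-to-voxel, with the fMRI activation to determine an optimal coil orientation and position". The choice follows: "The simulation that yields the highest correlation is selected the optimal coil position and orientation".

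Two other parts of Section 12 bear on this. The DWI fiber tracking paragraph uses tractography "to identify MT and all connecting regions (FEF, IPS"), with no ventral end point. In the E-field model itself, DWI has only an optional role: "Optionally, we can include anisotropic conductivity in the white matter based on the DWI data".

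**The concern.** The two rules differ in score and in output. Section 4 scores alignment with a tract and gives one orientation per pathway. Section 12 scores correlation with activation and gives one placement per participant. Section 12 neither refers back to the tract step nor says that Study 2 is treated differently. The words dorsal and ventral, and the labels rTMS-D and rTMS-V, do not occur in its text.

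The dorsal-versus-ventral contrast is the secondary objective. Section 2 predicts that rTMS-D improves motion performance while rTMS-V changes it little, if at all, so part of the prediction is a null. That null can be interpreted only if the ventral placement demonstrably differed from the dorsal one and reached its pathway. If staff follow different sections, or mix the two rules, the plan has no record from which to tell pathway specificity from failed targeting.

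**Working it through.** **1. The plan's own figure.** A 3×3 grid gives 3 × 3 = 9 positions. With 6 orientations, 9 × 6 = 54 simulations. This reproduces the stated 54.

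**2. What the Section 12 rule returns.** For each participant there is one score per simulation, and the maximum is taken. The maximum of one score over 54 candidates is 1 placement, barring ties. Because each candidate is a position-orientation pair, that placement fixes both.

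**3. What Study 2 needs.** Three spatial conditions less one control leaves 3 − 1 = 2 active placements, which must differ. The Section 12 rule supplies 1.

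**4. Whether the two rules can run in sequence.** If the correlation rule chose position only, 54 / 9 = 6 orientations would remain at the chosen position, and a tract score could pick one for each pathway. That would agree with Section 4, where fMRI gives the site and the tracts give the orientation. But Section 12 says that the correlation selects orientation too, so 1 candidate remains and the tract step has nothing to decide.

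**5. Whether Section 4 can be carried out alone.** It gives the criterion in words but no alignment score and no minimum separation. It says that Study 2 varies both location and orientation, yet its last step yields orientations only. The one computable rule in the document is the one in Section 12.

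**6. The tract list, side by side.**

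| Place | Dorsal end points | Ventral end point |
|---|---|---|
| Section 4, Study 2 | FEF | anterior temporal lobe |
| Section 12, DWI fiber tracking | FEF, IPS | none named |

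Section 2 gives FEF and IPS as examples of the dorsal pathway, so both regions in the SAP list are dorsal.

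**7. What cannot be computed.** The documents do not give the spacing of the 6 orientations, the angle between each participant's two tracts, or an overlap measure for the E-fields. The separation that would be achieved in practice therefore cannot be estimated from them.

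**The case against.** The strongest reply is that this is one combined document and Section 4 already defines the intervention. It traces both tracts in each participant, selects orientations for both pathways and requires three spatial conditions. Staff who must run three conditions could not follow the single-winner rule literally.

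The Section 12 rule also looks like shared text. The Concurrent TMS-EEG Procedure in Section 4, common to all three studies, identifies the MT target from fMRI activation and E-field modeling, and the only detailed account of that step is under the Study 2 heading in Section 12. The rule is scoped to all TMS during fMRI or EEG. The sentence before it concerns a recording target that no Study 2 procedure has, which suggests wording carried over from a wider project. The FEF and IPS list belongs to a paragraph on tractography and FA extraction, not on coil placement, and one reference cited there is on temporal-stem tracts. The figure cited for the grid was not available to this review and might show more.

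Much of this stands. A reader might infer from Section 12 that Study 2 has no dorsal-ventral manipulation, or that rTMS-D and rTMS-V will have zero separation. The documents do not support that, because it requires setting Section 4 aside. Nor does the FA list show that ventral tracts will be left out of targeting.

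What the reply does not remove is the conflict. If the rule is shared, it covers Study 2 and needs a stated exception, because it fixes orientation, which is the quantity that Section 4 leaves to the tracts. The text of Section 12 provides neither an exception nor a cross-reference.

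**Conclusion.** The point holds as a conflict between Sections 4 and 12, together with a missing operational criterion. Its size is structural: the SAP rule yields 1 placement where the secondary contrast needs 2 distinct ones, and the SAP tract list names 2 dorsal regions and no ventral one. This describes what the text produces if applied to Study 2 as written. It does not forecast what staff will do or how far apart the placements will be.

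The conclusion assumes that the Section 12 rule covers Study 2, as its heading and scope indicate, and that the missing figure does not add a tract step. If the investigators meant the rule only as the shared site-finding step, the design is sound in intent and the text needs to say so. The change should be made before Study 2 placements are computed. It does not affect the sample size or the error rate.

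**What to change.** Reconcile Section 4 (Study 2) with the DWI fiber tracking and E-field Modeling paragraphs of Section 12:

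- State that in Study 2 the highest-correlation rule does not set the rTMS-D and rTMS-V orientations, and that Section 4's tract-alignment criterion does. Say whether the correlation rule still sets the position.
- Have the investigators specify in advance the alignment score applied to the planned simulations for each pathway. The choice of score and of the resulting placement is theirs.
- Add the MT-to-anterior-temporal tract to the SAP tract list.
- Report for each participant the separation between rTMS-D and rTMS-V, as coil angle and E-field overlap, as a manipulation check. A small behavioural effect of rTMS-V can then be told apart from failed targeting.

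The simulations and DWI scans are already planned, so no new data are needed. The cost is SAP wording and a small amount of extra analysis time for the separation measures.
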